6. STUDY PROCEDURES AND ASSESSMENTS

A schedule for all procedures and evaluations to be conducted in this study is outlined in the visits schedule presented in

of this protocol.

6.1. Informed Consent

Each potentially eligible patient will be informed of the study objectives and overall requirements. Before conducting any of the screening tests, the Investigator or an authorized delegate will explain the study fully to the patient using the patient information leaflet/ICF. If the patient is willing to participate in the study, written informed consent will be requested after the patient has been given sufficient time to consider participation and the opportunity to ask for further details. The ICF will be signed and personally dated by both the patient and the Investigator or an authorized delegate. A copy of the signed consent form will be provided to the patient, and the original will be retained with the source documents.

A screening log will be completed for all patients who sign the ICF. These patients will be identified with their identification (ID) number; in addition, eventual reasons for exclusion from the study will be recorded.

6.2. Screening Visit (Day -14 to Day -1)

Each patient will be allocated a unique patient ID number, which will identify the patient throughout the study.

During the Screening visit, the following activities will be performed:

- Written informed consent will be obtained prior to performing any study related activities
- Inclusion/exclusion criteria will be checked.
- Each patient's demography: date of birth, gender, ethnicity, weight, height, medical history, and relevant baseline characteristics will be recorded.
- Historic and current prostate cancer related biopsies (prostate and metastatic sites) should be performed per local practice. All data related to date of biopsy, site of lesion, and pathology results will be collected in the database.
- ECOG performance status must be assessed (Section 11.1). The medical history will be recorded as well as all concomitant medications taken including therapies for PCa.
- All patients will have undergone histological/immunohistochemical exam at the time of the original PCa diagnosis and CT/MRI exam, within two months before enrollment.
- Vital signs will be assessed.
- ECG (12-lead) will be recorded.
- Blood samples for PSA, hematology, blood chemistry and urinalysis will be obtained.
- All concomitant medications including PCa therapies taken 2 weeks prior to the IP administration date through the end of study will be recorded.
- Any AEs occurring after the ICF signature will be recorded and followed until resolution.

6.3. Administration/ Imaging Period (Day 1)

Eligible patients who have met all inclusion criteria and none of the exclusion criteria will receive an injection of 3 MBq/Kg, but not less than 150 MBq and no more than 250 MBq of ⁶⁸Ga-PSMA-R2. Patient will enter the trial unit on the morning of the exam. Each subject will be allocated one single imaging kit.

- All concomitant medications including PCa therapies taken 2 weeks prior to the IP administration date through the end of study will be recorded.
- Any AEs occurring after the ICF signature will be recorded and followed until resolution.
- Vital signs will be assessed before and after the ⁶⁸Ga-PSMA-R2 injection and at the end of the PET/CT exam.
- ECOG performance status will be assessed.
- Patient will be injected intravenously one single bolus dose of ⁶⁸Ga-PSMA-R2.
- ECG (12-lead) will be recorded immediately after IP administration.

- For patients entering in Phase 1: PET/CT scans will be performed at approximately 20-30 minutes and at 1, 2, 3-4 hours post-injection.
- Patients in the Phase 1 portion of the study will undergo distribution/ dosimetry analysis
- For patients entering Phase 2, patients will have PET/CT imaging reduced to up to 2 whole body scans within the optimal time frame, to confirm the high tumor to background ratio, and agreement compared to standard conventional method.
- Samples for hematology, biochemistry and urinalysis will be collected after the administration of IP.
- Patients entering Phase 1 only: PK and dosimetry blood samples will be collected immediately prior to IP administration, approximately 5, 10, 20, 40 minutes, as well as immediately after, 1, 2, 4, and 6 hours post IP administration.
- Patients entering Phase 1 only: Urine sample for PK will be collected Pre-injection, approximately 0-20 minutes after IP administration, 0-1 hour, 1-2 hours, 2-4 hours, 4-6 hours post-injection.

6.4. Safety Follow-up Visits (Day 7 ± 2 Days and Day 28 ± 3 Days)

After IP administration, two safety follow-up visits will be performed on Day 7 (\pm 2 Days) and Day 28 (\pm 3 Days).

- All concomitant medications including PCa therapies taken 2 weeks prior to IP administration date through the end of study will be recorded.
- Any AEs occurring after the ICF signature will be recorded and followed until resolution.
- ECOG performance status is assessed.
- Vital signs will be assessed.
- Blood samples for hematology, biochemistry and urinalysis will be obtained.

6.5. Special Study Assessments

6.5.1. Histological / Immunohistochemical Assessment

All patients are required to have histological confirmation of adenocarcinoma of the prostate based on surgery/biopsy specimens of the primary tumor or the metastatic disease. Most recent biopsy sample collected should be used. All data related to date of biopsy, site of lesion, and pathology results will be collected in the database. No new biopsy is required for the purposes of this study.

6.5.2. CT/MRI/Bone Scan

All patients are required to undergo a CT/MRI within 2 months prior to enrollment. If a CT is performed, this should be a standard diagnostic thoracic and abdominopelvic CT scan, with a slice thickness of ≤ 5 mm; if MRI is performed, the injection of a contrast medium is recommended. Standard imaging modality for patients with PCa in biochemical relapse or with

metastatic disease, as applicable, will be performed as per routine institutional practice. Per RECIST v1.1 the imaging modality must be consistent throughout the study. Tumor assessment imaging procedures will be performed per local practice. CT scan is the preferred method and MRI will be done per local standard-of-care. Patients with either previous history of metastatic disease to the bone or any symptoms indicative of metastatic bone disease will require a bone scan.

All patients with metastatic prostate cancer enrolled in Phase 2 portion of the study will have their imaging procedures assessed locally for clinical management and centrally for comparison with ⁶⁸Ga-PSMA-R2 PET imaging.

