	 During the first part (Phase 1), approximately 6 patients with biochemically recurrent PCa will receive the investigational product (IP) and will remain at the site for approximately 6 hours post-injection in order to assess the PK, biodistribution vs. time, and dosimetry for critical organs. Patients will receive a single dose of 3 MBq/kg, (≥ 150 and ≤ 250 MBq), of ⁶⁸Ga-PSMA-R2 intravenously. Serial blood and urine samples will be collected for PK characterization and dosimetry and whole-body PET/CT will be acquired at selected time points (0-4 hours) to determine organ and tumor absorbed doses. Safety assessments will be conducted after IP administration on Day 1, and during follow-up on Days 7 and 28.
	• In the second part of the study (Phase 2), two groups of approximately 12 patients will be enrolled (patients with PCa in biochemical recurrence (PCa-BR), and patients with prostate cancer in the metastatic stage (mPCa)). Enrollment will be capped at 12 patients in each group to ensure an even distribution of patient conditions. If preliminary data analysis from the Phase 1 part of the study provides sufficient dosimetry data, all patients will undergo whole body PET/CT imaging optimized for time (up to 2 time points) according to the data analysis from the Phase 1 component of the study.
Study Population	Patients with histologically confirmed adenocarcinoma of prostate staged as PCa-BR or mPCa
Study Duration	Approximately 6 weeks: up to 2 weeks of screening assessment, a 1-Day IP administration and imaging period, and three safety follow-up visits, at least one hour after the administration, then 7 Days and 28 Days after the administration. End of the study is defined as the date the last patient enrolled completes the 28 Days safety follow-up.
Treatment Duration	One Day/single IP administration
Number of Patients	Approximately 30 patients will be enrolled in this trial.
Planned	Phase 1 will include approximately 6 patients with adenocarcinoma of prostate origin staged as PCa-BR.
	Phase 2 will be comprised of 2 groups: one of approximately 12 patients with PCa- BR and another of approximately 12 patients with mPCa.
Inclusion Criteria	1. Male patients, 18 years of age or older.
	2. Signed and dated written informed consent by the patient prior to any study- specific procedures
	3. Histologically confirmed adenocarcinoma of the prostate.

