techniques. Tumor uptake will be evaluated by SUV. SUV _{mean} and SUV _{max} will be
determined along with tumor to background ratio and these will be summarized
descriptively. Positive and negative lesions by the two imaging techniques will be
cross tabulated overall and by localization area on a lesion level and a patient level.
Agreement calculations will be performed on a patient level and tests of association
may be performed where appropriate.
Preliminary explorations of ⁶⁸ Ga-PSMA-R2 imaging performance relative to
cytology and/or historiathology findings from archival and/or recent bionsy
specimens will be performed for patients with bionsy data available
speemens will be performed for putents will blopsy dua dvalable.

STUDY PROCEDURES AND ASSESSMENTS

	Screening (Day -14 to Day -1 (+1 day)	Imaging Day 1 (+1 day)	Safety Follow-up Day 7 (+1 day)	Safety Follow-up Day 28 (+1 day)
Informed consent	X			
Inclusion/Exclusion Criteria Assessment	X			
Medical History & Demographics	Х			
ECOG Performance Status	X	Х	X	Х
Standard 12-lead ECG	X	Xª		
Disease Assessment: Imaging (CT/MRI or Bone Scan)	X ^b			
Vital Signs: Temperature (Temp), Blood Pressure (BP), Heart Rate (HR), and Respiratory Rate (RR) ^c	Х	Х	Х	Х
PSA	X			
Lab Analysis: Hematology, Blood Chemistry ^d	X	Х	Х	Х
Urine Analysis (Dipstick) ^e	X	Х	X	Х
⁶⁸ Ga-PSMA-R2 Administration		Х		
⁶⁸ Ga-PSMA-R2 PET/CT (Dosimetry) ^f		Х		
PK and Dosimetry Sample Collection (Blood) ^g		Х		
PK and Dosimetry Sample Collection (Urine) ^h		Х		
Adverse Event Collection	X	Х	X	Х
Concomitant Medications	X	X	X	Х

Table 1 Schedule of Procedures and Assessments

^a On Day 1, 12-Lead ECG will be collected after dosage administration.

^bAll patients are required to undergo a CT/MRI and bone scan if indicated (can be performed ≤ 2 months prior to study entry).

^c On Day 1 vital signs (temp, BP, HR, and RR) will be performed before and after to ⁶⁸Ga-PSMA-R2 injection and also at the end of ⁶⁸Ga-PSMA-R2 PET/CT scan.

^d Peripheral venous blood samples will be collected at each visit. On Day 1, blood samples will be collected after administration of ⁶⁸Ga-PSMA-R2.

^e A urine sample will be collected at each visit and analyzed at the clinical site if dipstick results are abnormal. Sample collection on Day 1 will be performed after the administration of IP

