4.1. Inclusion Criteria

- 1. Males, 18 years or older
- 2. Signed and dated written informed consent by the patient prior to any study-specific procedures.
- 3. Histologically confirmed adenocarcinoma of the prostate.
 - a. biochemical recurrence: defined as PSA is ≥ 0.2 ng/mL after radical prostatectomy or PSA nadir plus 2 ng/mL after radiation therapy with corresponding CT/MRI or bone scan revealing absence of local recurrence or metastatic lesions.

OR

- b. metastatic disease: defined as both, castration-sensitive or castration-resistant mPCa (presence of at least one metastatic lymph-node, visceral metastasis and/or bone metastasis).
- c. At least 2 weeks must have elapsed between last anti-cancer treatment administration and the administration of the imaging product, ⁶⁸Ga-PSMA-R2.
- 4. Prior major surgery must be at least 12 weeks prior to study entry.
- 5. Eastern Cooperative Oncology Group (ECOG) performance status 0-2, with a life expectancy ≥ 6 months.
- 6. Adequate bone marrow reserve and organ function as demonstrated by complete blood count, and biochemistry in blood and urine at Screening:
 - Hemoglobin (Hb): >8.0g/dL

- Platelet count of $> 50.000/\text{mm}^3$
- Serum creatinine < 1.5 ´ upper limit normal (ULN) or estimated glomerular filtration rate (eGFR) > 50 mL/min based upon The Chronic Kidney Disease Epidemiology Collaboration (CKD-EPI) equation.
- 8. For male patients with partners of childbearing potential, agreement to use barrier contraceptive method (condom) and to continue its use for 28 days after IP administration.

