5.6. Prohibited Concomitant Medications and Procedures

While participating in this study cancer targeted therapy including but not limited to chemotherapy, hormonal therapy (except for LHRH or GnRH), or external beam radiation is not permitted within four weeks prior to ⁶⁸Ga-PSMA-R2 PET/CT scan.

Any medications which are considered necessary for the patient's welfare, may be given at the discretion of the Investigator; however, if it belongs to the list above the patient will have to be withdrawn from the study treatment.

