5.1. ALL PATIENTS ENROLLED SET [ENR]

The all patients enrolled (ENR) set will contain all patients who provide informed consent for this study.

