15.2.2. LESIONS DETECTED BY PET SCAN AND/OR CONVENTIONAL SCAN, BY TBR

The number of positive lesions detected by PET scan, correlated or not with conventional scan, will be presented by TBR category.

15.2.3. BURDEN AND LOCATION OF TUMOR LESIONS DETECTED BY ⁶⁸Ga-PSMA-R2 IN COMPARISON WITH CONVENTIONAL IMAGING MODALITIES SUCH AS CT/MRI AND/OR BONE SCAN.

- The difference of number of lesions detected by ⁶⁸Ga-PSMA-R2 PET scan and by conventional scan modalities such as CT/MRI and/or bone scan, will be displayed by location. The number of lesions detected on the PET scan, correlated and not correlated with conventional scan lesions, will be presented. The number of lesions detected on the conventional scan, not correlated with lesions detected on the PET scan, will be presented.
- The difference in the number of positive patients detected by ⁶⁸Ga-PSMA-R2 PET and by conventional scan modalities such as CT/MRI and/or bone scan, will be displayed by location. The number of positive patients detected on the PET scan, with at least 1 lesion correlated, and at least 1 lesion not correlated with a lesion detected on the conventional scan, will be presented. The number of positive patients detected on the conventional scan, with no lesions correlated with any lesion detected on the PET scan, will be presented. Note: A positive patient has at least 1 lesion detected.

15.2.4. CALCULATION OF PATIENT LEVEL AGREEMENT OF ⁶⁸Ga-PSMA-R2 PET IMAGING WITH CONVENTIONAL IMAGING IN PROSTATE CANCER PATIENTS

The patient level agreement is commonly used to characterize the agreement of a new test with the non-reference standard. Here ⁶⁸Ga-PSMA-R2 PET scan is the new test and conventional scan is the non-reference Standard.

		Conventional Scan	
		+	-
⁶⁸ Ga-PSMA-R2 PET Scan	+	a	b
	-	c	d
Total		a+c	b+d

The patient-level positive percent agreement, negative percent agreement and overall percent agreement will be calculated based on the number of patients with at least one positive lesion detected by conventional scan and/or at least one positive lesion detected by PET scan.

Document: K:\AAA\Ga-PSMA-R2\VYA27826\ Biostatistics\Documentation\SAP\v2.0\Ga-PSMA-R2-SAP_v2.0
 Author:  Version Number: 2.0

Version Date: 29JUN2020

Template No.: CS_TP_BS016 Revision 5
 Effective Date: 01Apr2018

Reference: CS_WI_BS005

These percent agreements will be calculated as follows with their two-sided 95% score confidence intervals:

- Positive percent agreement: $a/(a+c) * 100$

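### The comparator CT/MRI or bone scan may precede PET by up to about 75 days with new therapy allowed in between, and the agreement analysis cannot separate treatment effects from a difference between the tests

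*Protocol*

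**What the plan says.** **Timing of the comparator.** Protocol 6.5.2 states: "All patients are required to undergo a CT/MRI within 2 months prior to enrollment". Section 6.2 gives the same window. Footnote b of the schedule table applies it to CT/MRI and, if indicated, bone scan: "can be performed ≤ 2 months prior to study entry". The synopsis then allows "up to 2 weeks of screening assessment, a 1-Day IP administration and imaging period", and the schedule table gives Day 1 a one-day window. No text limits the interval from conventional scan to PET, or requires a repeat scan if treatment changes.

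**Treatment restrictions.** Inclusion criterion 3c: "At least 2 weeks must have elapsed between last anti-cancer treatment administration and the administration of the imaging product". Section 5.6 says that listed cancer therapy, with LHRH and GnRH exempt, "is not permitted within four weeks prior to" the PET/CT. The two periods conflict and must be reconciled. Neither is tied to the date of the conventional scan.

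**Analysis.** SAP 15.2.3 reports PET lesions with and without a conventional match, and also the reverse: "The number of lesions detected on the conventional scan, not correlated with lesions detected on the PET scan, will be presented". SAP 15.2.4 puts unmatched PET findings in cell b and unmatched conventional findings in cell c, at patient and lesion level. SAP 6.5 applies no visit windows and SAP 7.5 plans no subgroups. SAP 15.1 places conventional scans on Day 1 alongside PET, which does not agree with protocol 6.5.2.

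**The concern.** Agreement between two tests can be interpreted only if both look at the same disease. Here the first test may be two months or more older than the second, and a patient may start a systemic agent or receive radiotherapy after the first test and still satisfy either restriction. A metastasis seen on CT and cleared before PET is counted in cell c. A lesion that appears after the CT is counted in cell b. Neither reflects how PET performs.

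Per-patient agreement with conventional imaging is a stated secondary objective, and positive agreement depends on about 12 patients, so one or two such cases would be visible in the result. The per-protocol set does not help, because these patients have followed the protocol.

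**Working it through.** **The plan's own figure.** Protocol 8.1 gives 66.4% to 92.7% for 25/30. The Wilson score interval is [p + z²/2n ± z√(p(1−p)/n + z²/4n²)] / (1 + z²/n). With p = 0.8333, n = 30 and z = 1.96 it gives 66.4% to 92.7%, an exact match. This figure does not bear on the scan interval; it fixes the method for the intervals below.

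**Longest permitted gap.**
- Two months: 2 × 30.4375 = 60.9 days (59 to 62 by calendar).
- Day −14 to Day 1, with no Day 0 as in SAP 6.2: 14 days.
- Enrolment at consent or screening: 60.9 + 14 = 74.9 days (73 to 76 by calendar; 74 to 77 with the one-day imaging window).
- Enrolment on injection day: 60.9 days.

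The protocol does not define enrolment. SAP 5.1 supports the first reading, since its enrolled set "will contain all patients who provide informed consent for this study".

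**Part of the gap open to treatment.**

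| Enrolment means | Gap (days) | 2-week rule | Four-week rule |
|---|---|---|---|
| Consent or screening | 74.9 | 74.9 − 14 = 60.9 | 74.9 − 28 = 46.9 |
| Injection day | 60.9 | 60.9 − 14 = 46.9 | 60.9 − 28 = 32.9 |

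Treatment between the scans is possible in all four cells.

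**Effect on patient-level positive agreement, a/(a+c).** Assume all 12 mPCa patients are positive on both scans apart from the effect in question. Two kinds of affected patient arise:
- All PET-positive disease is lost: the patient moves from a to c.
- One conventional lesion is lost but another lesion stays PET-positive: under the literal definitions in SAP 15.2.4 the patient counts in both a and c.

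The documents give no count of affected patients, so 1 to 3 is an assumed range.

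| Patients affected | Moves from a to c (95% score interval) | Counts in both a and c |
|---|---|---|
| 0 | 12/12 = 100% (75.8 to 100) | 12/12 = 100% |
| 1 | 11/12 = 91.7% (64.6 to 98.5) | 12/13 = 92.3% |
| 2 | 10/12 = 83.3% (55.2 to 95.3) | 12/14 = 85.7% |
| 3 | 9/12 = 75.0% (46.8 to 91.1) | 12/15 = 80.0% |

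The first affected patient costs 8.3 or 7.7 points.

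**Effect on negative agreement, d/(b+d).** There are about 6 + 12 = 18 PCa-BR patients, conventional-negative by eligibility. Each one who becomes PET-positive only through a new lesion costs 1/18 = 5.6 points.

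**The case against.** The strongest case against is that this is a design choice on a secondary, descriptive endpoint that the protocol calls preliminary. There is no formal testing, and the SAP calls conventional imaging a non-reference standard, so disagreement is not scored as PET error. Results are also shown separately for PCa-BR and mPCa. All of this stands and limits the weight of the point.

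Other parts of the objection also stand:
- Major surgery must be at least 12 weeks before study entry, which is longer than the scan look-back, so major surgery between scan and entry is already excluded.
- In PCa-BR, protocol section 1 says a PSA rise precedes clinically detectable recurrence by months to years and reports limited CT/MRI sensitivity. PET-positive, conventional-negative results are therefore expected from detection alone, and nothing shows that growth over 75 days adds materially.
- A loss of 8.3 points needs all PET-positive disease in a patient to disappear.

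A reader might infer that every treated or progressed lesion is counted as disagreement. It is not: a lesion that grows or shrinks and still matches stays in cell a.

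A reader might also infer that the main table should be limited to patients with no anti-cancer drug between the scans. That would remove mPCa patients on continuing LHRH or GnRH, which section 5.6 exempts, even though nothing changed between their scans. It could take out many of the 12.

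The Day 1 wording in SAP 15.1 might seem to remove the gap. It does not, because the only Day 1 CT in protocol 6.5.4 is low-dose and without contrast, for localization and attenuation correction.

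**Conclusion.** The point holds in a limited form. The comparator can be up to about 75 days old at PET (about 61 if enrolment is injection day), treatment can start in between under either restriction, and the SAP has no means of separating the resulting disagreement from a difference between the tests. Only lesions cleared or newly appeared between the scans matter.

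The main exposure is positive agreement in about 12 mPCa patients, at roughly 7.7 to 8.3 points for the first affected patient. This assumes that all 12 are otherwise positive on both scans. How many patients are affected is unknown, so a total loss of, say, 25 points is an illustration of three patients and not a finding. The primary safety objective is untouched. This is a worthwhile low-cost addition and not a condition for a valid analysis.

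**What to change.** 1. Keep the all-patient agreement table as planned.
2. Pre-specify in SAP 15.2.3 and 15.2.4 the same analysis without patients who, between the conventional scan and PET, started or changed systemic anti-cancer therapy, or had radiotherapy or a procedure to a lesion. Continuing unchanged therapy, including stable LHRH or GnRH, is not a reason for exclusion. The flag uses dates and not scan results, so it does not select on agreement.
3. List each patient's scan-to-PET interval.
4. Check the data first. Imaging results come from a vendor outside the CRF (SAP 15), and no section lists the conventional scan date as a supplied variable. Protocol 6.2 to 6.4 require PCa therapies to be recorded only from 2 weeks before injection. Earlier therapy may be in the medical history and in the prior therapy, procedure and radiotherapy pages used in SAP 12, but complete dates back to the scan need confirming. The partial-date rules in SAP Appendix 2 could misplace an event within a window of weeks, so report patients whose status cannot be settled.
5. Reconcile criterion 3c with section 5.6, and SAP 15.1 with protocol 6.5.2, and state what enrolment means.

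The cost is SAP wording, one derived flag, one listing and one extra table on fewer patients with wider intervals. If dates are missing, sites or the imaging vendor would have to be queried.

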6.5.4. Imaging assessments

6.5.4.1. Imaging Procedure During the Phase 1 Portion of the Study

⁶⁸Ga-PSMA-R2 PET/CT imaging (four scans) will be performed using a standard integrated PET/CT system. Patients will be placed on the scanner table to allow a vertex to mid-thigh low-dose CT scan without contrast (used for anatomic localization and attenuation correction), followed immediately by emission scan after ⁶⁸Ga-PSMA-R2 injection. PET scans will be performed from vertex to mid-thigh in 3D (3-dimentional acquisition) mode. Please refer to Section 6.5.4.2 for more details.

Maximum standardized uptake values (SUV_{max}) will be used to determine the tumor lesions, defined as focal areas of abnormal uptake showing a higher SUV_{max} than surrounding tissue.

Identification of the time points post-injection with the highest observed number of lesions and the highest SUV_{max} , SUV_{mean} values and the tumor to background ratios for each SUV will be determined. The later will be conducted separately for each imaging time point (20-30 minutes, 1, 2, 3-4 h) post-injection through qualitative visual analysis of total number of lesions identified by PET, and semi-quantitative analysis by means of SUV_{max} and SUV_{mean} values and time point will be conducted.

Lesions suggestive of PCa will be counted and analyzed for radioactive uptake (expressed as SUV_{mean} and SUV_{max}) and localization. Any PCa lesion will be counted and analyzed. Tumor contrast will be measured by dividing the SUV_{mean} of tumor lesions by the SUV_{mean} of the background (e.g. gluteal musculature) and by dividing the SUV_{max} of tumor lesions by the SUV_{mean} of the SUV_{mean} of the background.

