6.5.4.3. Whole Body PET/CT Imaging for Phase 2 Portion of the Study

Preliminary data analysis from the Phase 1 portion of the study will provide sufficient dosimetry data, therefore all Phase 2 patients will have PET/CT imaging reduced to up to 2 whole body

scans within the optimal time frame, to confirm the high tumor to background ratio, and agreement compared to standard conventional method.

⁶⁸Ga PSMA-R2 PET/CT imaging will be performed using a standard integrated PET/CT system. Patients will be placed on the scanner table to allow a vertex to mid-thigh low-dose CT scan without contrast (used for anatomic localization and attenuation correction), followed immediately by emission imaging after ⁶⁸Ga-PSMA-R2 injection. A non-contrast-enhanced CT will be performed using routine investigational site imaging parameters. Immediately after CT scanning, PET scan will be performed from vertex to mid thighs in 3D (3-dimensional acquisition) mode. The scan duration will be 3 min for each bed position. The emission data will be corrected for dead-time, scatter, and decay, and resulting voxels were stored in units of Bq/mL. Attenuation correction will be performed using low-dose non-enhanced CT data acquired at each time point.

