15. BIODISTRIBUTION, DOSIMETRY AND IMAGING OF ⁶⁸GA-PSMA-R2

Biodistribution is defined as the activity in various organs over time quantified by imaging. Dosimetry is the assessment of radiation dose per unit administered activity.

Document: K:\AAA\Ga-PSMA-R2\VYA27826\ Biostatistics\Documentation\SAP\v2.0\Ga-PSMA-R2-SAP_v2.0
 Author:  Version Number: 2.0

Version Date: 29JUN2020

Template No.: CS_TP_BS016 Revision 5
 Effective Date: 01Apr2018

Reference: CS_WI_BS005

Biodistribution, dosimetry and imaging data are not collected in the CRF. Biodistribution and dosimetry data will be received from the principal scientist of a third-party radiation dosimetry vendor while imaging data will directly be sent from a third-party medical imaging vendor. Results from the radiation dosimetry vendor will be included in the reporting of Phase I of this study. Results from the medical imaging vendor will be included in the reporting of Phase I and II of this study. The analysis of imaging data will also be performed on patients from Phase I.

The terminology, conventional scans and standard imaging, both relate to CT, MRI and/or bone scans.

A list of tests and organs to be included in the outputs is included in APPENDIX 5.

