- Negative percent agreement: $d/(b+d) * 100$
- Overall percent agreement: $(a+d)/(a+b+c+d) * 100$

Where

- a is the number of patients with at least one positive lesion detected by conventional scan and at least one positive lesion detected by PET scan
- b is the number of patients with at least one positive lesion detected by PET scan that is not correlated with conventional scan
- c is the number of patients with at least one positive lesion detected by conventional scan that is not correlated with PET scan
- d is the number of patients with no lesions detected by conventional scan or PET scan

These 3 coefficients and their 95% Clopper Pearson Exact confidence intervals will be calculated using SAS PROC FREQ as follow:

```
PROC FREQ data=temp;
  tables resp/binomial (exact level='1');
RUN;
```

The lesion-level positive percent agreement and overall percent agreement will be calculated based on the number of lesions detected as positive by conventional scan and/or by PET scan.

These percent agreements will be calculated as follows with their two-sided 95% score confidence intervals:

- Positive percent agreement: $a/(a+c) * 100$
- Overall percent agreement: $(a)/(a+b+c) * 100$

Where

- a is the number of lesions detected as positive in both PET and conventional scan
- b is the number of lesions detected as positive in PET scan but not correlated with conventional scan
- c is the number of lesions detected as positive in conventional scan but not correlated with PET scan

These 2 coefficients and their 95% Clopper Pearson Exact confidence intervals will be calculated using SAS PROC FREQ as above.

Document: K:\AAA\Ga-PSMA-R2\VYA27826\Biostatistics\Documentation\SAP\v2.0\Ga-PSMA-R2-SAP_v2.0
 Author:  Version Number: 2.0

Version Date: 29JUN2020

Template No.: CS_TP_BS016 Revision 5
 Effective Date: 01Apr2018

Reference: CS_WI_BS005

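### PET lesions outside the required CT field count as disagreement with conventional imaging, although in patients without a bone scan no required conventional test covers the site

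*Protocol*

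**What the plan says.** **PET field.** Protocol 6.5.4.1 states for Phase 1: "PET scans will be performed from vertex to mid-thigh in 3D (3-dimentional acquisition) mode". Protocol 6.5.4.3 states for Phase 2: "PET scan will be performed from vertex to mid thighs in 3D (3-dimensional acquisition) mode".

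**Conventional field.** Protocol 6.5.2 requires a CT or MRI within two months before enrollment. A CT is to be a "standard diagnostic thoracic and abdominopelvic CT scan". The extent of an MRI is not given: "CT scan is the preferred method and MRI will be done per local standard-of-care". Bone scan is conditional: "Patients with either previous history of metastatic disease to the bone or any symptoms indicative of metastatic bone disease will require a bone scan". Footnote b of the Protocol's Table 1 likewise makes it dependent on indication.

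**Comparator.** SAP 15 pools the modalities: "The terminology, conventional scans and standard imaging, both relate to CT, MRI and/or bone scans".

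**Agreement cells.** At lesion level SAP 15.2.4 says "b is the number of lesions detected as positive in PET scan but not correlated with conventional scan", and c is the mirror image. At patient level, one uncorrelated PET lesion is enough for b. Neither document asks whether the other test imaged the site, provides a not-evaluable category, or splits the rates by whether a bone scan was done.

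**The concern.** A site that no conventional test imaged is scored as if conventional imaging had looked there and found nothing. The resulting disagreement reflects scan extent, not how the tracer performs. Part of any shortfall in agreement could then be wrongly read as PET finding lesions that conventional imaging missed, or as PET false positives.

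Patient-level agreement is a named secondary objective and endpoint, and Phase 2 imaging is partly meant to confirm it. Negative agreement is the most exposed rate. Biochemical-recurrence patients enter with conventional imaging that shows no lesion (Protocol 4.1), so a single out-of-field PET lesion can change their classification.

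**Working it through.** **Inputs**
- Planned patients: 6 biochemical-recurrence patients in Phase 1, then 12 biochemical-recurrence and 12 metastatic patients in Phase 2. That makes 6 + 12 = 18 biochemical-recurrence patients out of 30 (Protocol synopsis and 3.1).
- Lesion-level formulas (SAP 15.2.4): overall agreement a/(a+b+c); positive agreement a/(a+c).
- Patient-level formulas (SAP 15.2.4): negative agreement d/(b+d); overall agreement (a+d)/(a+b+c+d).
- Number of lesions outside the shared field: not in the documents, so assumed below and shown as a range.

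**The plan's own figure.** Protocol 8.1 gives 25/30 = 83.3% with a 95% interval of 66.4% to 92.7%. The Wilson score interval with z = 1.96 has centre (0.8333 + 3.8415/60)/(1 + 3.8415/30) = 0.7955. Its half-width is 1.96 × √(0.8333×0.1667/30 + 3.8415/3600)/(1 + 3.8415/30) = 0.1311. The result is 66.4% to 92.7%, so the figure reproduces.

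**Who is exposed.** The case the documents establish is a patient with CT and no bone scan. PET then covers the head, the neck and the thigh down to its middle. The required CT covers thorax, abdomen and pelvis; its exact upper and lower limits are not given.

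**Lesion level.** Assume a = 45, b = 5, c = 5 within the shared field, and add m PET-only lesions outside it. These all go to b:

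| m | Overall agreement | Positive agreement |
|---|---|---|
| 0 | 45/55 = 81.8% | 45/50 = 90.0% |
| 1 | 45/56 = 80.4% | 45/50 = 90.0% |
| 5 | 45/60 = 75.0% | 45/50 = 90.0% |

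Positive agreement does not contain b, so it does not move. More generally, if in-field agreement were perfect, overall agreement would equal 1 − f, where f is the share of all lesions lying outside the shared field: 95%, 90% and 80% for f of 5%, 10% and 20%.

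**Patient level.** Take a patient with no conventional lesion whose only PET lesion is out of field. That patient sits in b, but would sit in d on the shared field.
- Overall agreement loses 1/30 = 3.3 points per such patient.
- Negative agreement loses 1/18 = 5.6 points if b+d consists of the 18 biochemical-recurrence patients. This assumes that the study reads match entry status.
- From the Protocol's 25/30, if one, two or all five disagreements were of this kind, shared-field agreement would be 26/30 = 86.7% (Wilson 70.3% to 94.7%), 27/30 = 90.0% (74.4% to 96.5%) or 30/30 = 100% (88.6% to 100%).

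**A complication.** The patient-level cells overlap. A patient with one correlated lesion and one PET-only lesion satisfies both a and b, and the SAP does not say which takes precedence. In patients positive on both tests, the effect of an out-of-field lesion depends on that unstated rule.

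**The case against.** Several points on the other side have force.

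- **Agreement with conventional imaging as performed is a legitimate target.** The SAP does not treat conventional imaging as a reference standard, and Protocol 6.5.2 leaves it to routine practice. This stands: the restricted analysis answers a different question and belongs beside the planned one.
- **Results are already shown by location.** SAP 15.2.3 does this for lesion and patient counts, so a skull or neck lesion would be visible there. The rates and intervals in 15.2.4 remain unrestricted.
- **SAP 15.1 refers to whole-body conventional scans at the PET time points.** This conflicts with Protocol 6.5.2, where CT/MRI precedes enrollment. It may mean the low-dose CT of the PET session, which Protocol 6.5.4.1 and 6.5.4.3 use for localization and attenuation correction. It needs reconciling and does not settle coverage.
- **In biochemical recurrence, entry criteria already drive the result.** If the study reads match entry status, any PET-positive patient there falls in b wherever the lesion lies. This stands; coverage is only one cause of disagreement.

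A reader might go further and infer that conventional-only lesions outside the PET field inflate c and depress positive agreement. Such lesions are possible, but neither document states the coverage of bone scan or MRI. A reader might also infer that without a bone scan the skeleton is not imaged at all. Protocol 1 names CT among the techniques for detecting bone metastasis. Inside the CT field, a missing bone scan therefore makes the comparator's sensitivity uneven; it does not leave bone unimaged.

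**Conclusion.** The point holds in one direction. In patients with CT and no bone scan, PET lesions in the head, neck or upper thigh are scored as disagreement where no required conventional test looked. That lowers lesion-level overall agreement and patient-level negative and overall agreement. The documents establish the mechanism but not its frequency; every percentage for the size of the effect is conditional on the assumed counts above.

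The stakes are moderate. These analyses are secondary and descriptive, and the primary safety objective is untouched. With about 30 patients, though, one or two misattributed patients visibly shift a reported rate, and the correction needs no new scan or reader. It is worth making before the imaging tables are produced.

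**What to change.** In SAP 15.2.4:
1. Add lesion- and patient-level agreement restricted to regions imaged by both PET and at least one conventional scan in that patient. Report it beside the planned unrestricted rates.
2. List lesions outside the shared field separately as 'not evaluable by comparator'.
3. Show bone-lesion agreement by whether a bone scan was done. Within the CT field, describe any difference as uneven comparator sensitivity, not absent coverage.
4. Obtain from the imaging vendor a coverage flag for each patient, giving modality and anatomical extent. Lesion location alone is not enough, because MRI extent and bone-scan use vary between patients.
5. Reconcile SAP 15.1 with Protocol 6.5.2 on which conventional scans are meant, when they are done and what they cover.

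The cost is SAP wording, one additional table and a small data request. SAP 15 says imaging data are not collected in the CRF, and neither document confirms that scan extent is already delivered. The restricted table will also contain fewer lesions.
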